#### **14.4 Exclusion of Women, Minorities, and Children (Special Populations)**

This trial will be inclusive of female and male adults who meet the subject inclusion/exclusion criteria, regardless of religion or ethnic background. Should the outcome of this trial be deemed acceptable, additional trials may be initiated in other populations.

#### **14.5 Subject Confidentiality**

Subjects will have code numbers and will not be identified by name. Subject confidentiality is strictly held in trust by the participating site PIs, their study personnel, the sponsor(s), and their agents. This confidentiality is extended to cover testing of biological samples, in addition to the clinical information relating to subjects.

The study protocol, documentation, data, and all other information generated will be held in strict confidence. No information concerning the trial or the data will be released to any unauthorized third party without prior written approval of the sponsor.

All information provided by the sponsor and all data and information generated by the participating site as part of the trial (other than a subject's medical records) will be kept confidential by the site PI and other study personnel to the extent permitted by law. This information and data will not be used by the site PI or other study personnel for any purpose other than conducting the trial. These restrictions do not apply to: (1) information that becomes publicly available through no fault of the site PI or other study personnel; (2) information that is necessary to disclose in confidence to an IRB solely for the evaluation of the trial; (3) information that is necessary to disclose in order to provide appropriate medical care to a study subject; or (4) study results that may be published as described in Section 16. If a written contract for the conduct of the trial that includes confidentiality provisions inconsistent with this statement is executed, that contract's confidentiality provisions shall apply rather than this statement.

The study monitor, applicable regulatory authorities, such as the FDA, or other authorized representatives of the sponsor may inspect all documents and records required to be maintained by the site PI. This includes, but is not limited to, medical records (office, clinic, or hospital) and pharmacy records for the subjects in this trial. The participating sites will permit access to such records.

To protect privacy, a Certificate of Confidentiality (CoC) has been obtained. With this CoC, the researchers cannot be forced to release information that may identify the research subject, even by a court subpoena, in any federal, state, or local civil, criminal, administrative, legislative, or other proceedings. The researchers will use the CoC to resist any demands for information that would identify the subject, except as explained below.

The CoC cannot be used to resist a demand for information from personnel of the US Government that is used for auditing or evaluation of federally funded projects, like this trial, or for information that must be released in order to meet the requirements of the FDA.

A CoC does not prevent subjects from voluntarily releasing information about themselves or their involvement in this research. If any person or agency obtains a written consent to receive research information, then the researchers may not use the CoC to withhold that information.

The CoC does not prevent the researchers from reporting, without the subject's consent, information that would identify the subject as a participant in the research project regarding matters that must be legally reported, including: child and elder abuse, sexual abuse, or wanting to harm themselves or others.

## **14.6 Study Discontinuation**

If the trial is discontinued, subjects who sign the ICF and are randomized and treated will continue to be followed for safety assessments. No further study drug will be administered

## 14.7 Future Use of Stored Specimens

Subjects will be consented to have leftover serum stored for future testing. Storage of samples for future testing is optional and is not a requirement for participation in the study. If the subject consents to storage and future use of specimens, specimens will be kept at the Central Laboratory (University of Alabama at Birmingham). Subjects will not be contacted with the results of these future research studies. Future testing on specimens will only occur to the extent authorized in each study site's ICF or as otherwise authorized under applicable law and after review and approval by DMID and the IRB of the researcher requesting the specimens.

Archived specimens will be identified only by the subject number and visit number, which will allow linkage of the specimens to study data but not to any personal identifiers.

There will be no direct benefit to subjects from allowing specimens to be stored and used for future purposes. However, the results may provide information that will help in the diagnosis or treatment of future patients.

Subjects' specimens will be kept until they are used up or destroyed. They may be used to develop new tests or products. In some instances, these may have potential commercial value. If a subject decides at any time that s/he does not want specimens stored for future research, s/he must contact the study staff who will then notify the laboratory/specimen archive staff, who will mark the specimens by adding a "destroy" label. Labeled specimens will be destroyed at the end of this study or will be removed from storage and destroyed as soon as possible.

---

## **15 DATA HANDLING AND RECORD KEEPING**

The site PI is responsible for ensuring the accuracy, completeness, legibility, and timeliness of the data reported.

Data collection forms will be derived from the eCRFs and provided by the SDCC to record and maintain data for each subject enrolled in the study. All data collection forms should be completed in a neat, legible manner to ensure accurate interpretation of data. Black or blue ink is required to ensure clarity of reproduced copies. When making a change or correction, cross out the original entry with a single line and initial and date the change. Do not erase, overwrite, or use correction fluid or tape on the original.

Data reported in the eCRFs derived from the data collection forms should be consistent with the data collection forms, or the discrepancies should be explained.

The sponsor and/or its designee will provide guidance to site PIs and other study personnel on making corrections to the data collection forms and eCRFs.

### **15.1 Data Management Responsibilities**

All data collection forms and laboratory reports must be reviewed by the clinical team and data entry personnel, who will ensure that they are accurate and complete. AEs must be recorded on the appropriate data collection form, assessed for severity and relationship, and reviewed by the site PI or appropriate sub-investigator.

Data collection is the responsibility of the study personnel at the participating sites under the supervision of the respective site PI. During the study, the site PI must maintain complete and accurate documentation for the study.

The SDCC for this study will be responsible for data management, quality review, analysis, and reporting of the study data.

### **15.2 Data Capture Methods**

Clinical (including, but not limited to, AEs/SAEs, concomitant medications, medical history, physical assessments, and clinical laboratory values), and immunogenicity data will be entered into a 21 CFR 11-compliant Internet Data Entry System, Advantage eClinical®, provided by the SDCC. The data system includes password protection and internal quality checks, such as automatic range checks, to identify data that appear inconsistent, incomplete, or inaccurate. Clinical data will be entered directly from the data collection forms completed by the study personnel.

### **15.3 Types of Data**

Data for this study will include clinical, safety, and outcome measures (e.g., clinical laboratory values and immunogenicity data).

### **15.4 Timing/Reports**

A final report will be prepared following the availability of all the safety and laboratory data. Interim statistical reports may be generated as deemed necessary and appropriate by DMID. Safety and laboratory data summary reports may be generated for the DSMB.

After full analysis and final CSR reporting is complete, and upon request and DMID approval, the SDCC will provide the participating sites with a summary of results by treatment group. The participating sites requesting such information to share with study subjects must do so in compliance with their respective IRB guidelines.

### **15.5 Study Records Retention**

Records and documents pertaining to the conduct of this study, including data collection forms, source documents, ICFs, laboratory test results, and medication inventory records, must be retained by the investigator for at least 2 years following the completion of this study. No records may be destroyed without written permission from the sponsor.

### **15.6 Protocol Deviations**

A protocol deviation is any noncompliance with the clinical trial protocol, GCP, or protocol-specific MOP requirements. The noncompliance may be either on the part of the subject, the site PI, or the study site staff. As a result of deviations, corrective actions are to be developed by the site and implemented promptly.

These practices are consistent with ICH E6:

4.5 Compliance with Protocol, sections 4.5.1, 4.5.2, and 4.5.3

5.1 Quality Assurance and Quality Control, section 5.1.1

5.20 Noncompliance, sections 5.20.1, and 5.20.2.

It is the responsibility of the site PI to use continuous vigilance to identify and report deviations within 5 working days of identification of the protocol deviation, or within 5 working days of the scheduled protocol-required activity. All deviations must be promptly reported to DMID, via the SDCC's Advantage eClinical®.

Note: Those sites participating in trials with a designated 'central unit' will follow the reporting requirements specified in their protocols and MOPs. The 'central unit' will be responsible for submission of the protocol deviation information to TRI-ICON/DMID-CROMS.

All protocol deviations, as defined above, must be addressed in study subject data collection forms. A completed copy of the DMID Protocol Deviation Form must be maintained in the regulatory file, as well as in the subject's study chart. Protocol deviations must be sent to the local IRB per their guidelines. The site PI and other study personnel are responsible for knowing and adhering to their IRB requirements.

---

## 16 PUBLICATION POLICY

All investigators funded by the NIH must submit or have submitted for them to the National Library of Medicine's PubMed Central (<http://www.ncbi.nlm.nih.gov/pmc/>) an electronic version of their final, peer-reviewed manuscripts upon acceptance for publication, to be made publicly available no later than 12 months after the official date of publication. The NIH Public Access Policy ensures the public has access to the published results of NIH-funded research. It requires investigators to submit final peer-reviewed journal manuscripts that arise from NIH funds to the digital archive PubMed Central upon acceptance for publication. Further, the policy stipulates that these papers must be accessible to the public on PubMed Central no later than 12 months after publication.

Refer to:

- NIH Public Access Policy, <http://publicaccess.nih.gov/>
- NIH Office of Extramural Research (OER) Grants and Funding, <http://grants.nih.gov/grants/oer.htm>

As of January 2018, all clinical trials supported by the NIH must be registered on ClinicalTrials.gov no later than 21 days after the enrollment of the first subject. Results of all clinical trials supported by the NIH generally need to be submitted no later than 12 months following the primary completion date. A delay of up to 2 years is available for trials that meet certain criteria and have applied for certification of delayed posting.

As part of the result posting, a copy of this protocol (and its amendments) and a copy of the Statistical Analysis Plan will be posted on ClinicalTrials.gov.

For this trial, the responsible party is DMID, which will register the trial and post results.

The responsible party does not plan to request certification of delayed posting.

Refer to:

- Public Law 110-85, Section 801, Clinical Trial Databases
- 42CFR11
- NIH NOT-OD-16-149

**APPENDIX A: SCHEDULE OF EVENTS**

Procedures		Visit 1 – Screening/ Enrollment (Day 1)	Contact (approx. 24 hours after Visit 1)	Visit 2 (Week 1 – Day 7 to 13)	Visit 3 (Week 2 – 6 to 12 days after Visit 2)	Visit 4 (Month 1 – Day 30 ± 7 days)	Visit 5 (Month 3 – Day 90 ± 21 days)	Visit 6 (Month 6 – Day 180 ± 21 days)	Visit 7 (Month 9 – Day 270 ± 28 days)	Visit 8 (Month 12 – Day 360 ± 28 days)	Early Termination	Unscheduled Visit 
Informed consent		X										
Demographics		X										
Eligibility criteria		X										
Medical history 		X		X	X	X	X	X	X	X	X	X
Sexual history 		X		X	X	X	X	X	X	X	X	X
Targeted physical exam 		X		X	X	X	X	X	X	X	X	X
Pregnancy test 		(X)		(X)	(X)	(X)	(X)	(X)	(X)	(X)	(X)	(X)
Concomitant medications 		X		X	X	X	X	X	X	X	X	X
Specimen collection	RPR titer	X		X	X	X	X	X	X	X	X	
	Storage	X		X	X	X	X	X	X	X	X	
	CD4 count 	(X)				(X)		(X)		(X)	(X)	
	HIV testing 	(X)					(X)	(X)	(X)	(X)	(X)	
	Other STI screening/ diagnosis 	X		(X)	(X)	(X)	(X)	(X)	(X)	(X)	(X)	(X)
	Oral cavity and lesions (if present) swabbed 	(X)		(X)	(X)	(X)	(X)	(X)	(X)	(X)	(X)	(X)
Randomization		X										
BPG administered 		X		(X)	(X)							
Contact information collected/reviewed 		X		X	X	X	X	X	X	X	X	X
Jarisch-Herxheimer checklist 		X	X	(X)								
Jarisch-Herxheimer reaction assessed 			X	(X)								
Resolution of syphilis signs assessed				X	X							
AEs/SAEs assessed 		X		X	X	X						X

(X) – As indicated/appropriate. Refer to footnotes below and protocol Section 7.

 At Visit 1, collect complete medical history (including review of medical records for the past 14 days, if available). At subsequent visits, review medical history (including interval medical records, if available) and update as appropriate.

 At Visit 1, collect sexual history for the past 60 days. At subsequent visits, collect interim sexual history since last visit.

 Targeted physical exam includes vital signs: temperature, heart rate, respiration rate, and blood pressure; and genital, rectal, oral, skin, and lymph node examinations.

 Perform on subjects of childbearing potential. At Visit 1, urine or serum pregnancy test is permitted. At subsequent visits, perform urine pregnancy test.

 At Visit 1, record concomitant medications taken in the last 30 days before initiating BPG. At subsequent visits, record all concomitant medications taken since the last visit and update previously recorded medications as appropriate.

 Collect for subjects with known HIV infection whose medical records do not include a CD4 count in the past 30 days; at Visit 4, this is only applicable to subjects newly found to have HIV infection from Visit 1 to Visit 4 (inclusive).

 Perform for subjects who do not have a previously documented positive HIV test result using locally available tests (e.g., nucleic acid tests (NATs), antibody/antigen tests).

 At Visit 1, collect specimens at sites of exposure for screening/diagnosis of chlamydia and gonorrhea for all subjects who have not been tested since last sexual activity and for all subjects who have been sexually active in the past 14 days and for other STIs as indicated by local standard of care and subject history. At subsequent visits, collect specimens at sites of

exposure for STI testing per local standard of care and subject history.

It is optional to swab subject's oral cavity and lesions, if lesions are present. See Section 8.2.2.

 At Visit 1, administer BPG to all subjects. At Visits 2 and 3, administer BPG to subjects in Arm 2 only.

At Visit 1, collect contact information. At subsequent visits, review contact information and update if needed.

 Distribute checklist at Visit 1. Subject refers to completed checklist during Jarisch-Herxheimer assessment; see Sections 7 and 8.1.

Assess per protocol Section 8.1. If subject is not reached, assess at Visit 2.

 Assess and record all AEs/SAEs (including solicited reactogenicity AEs and other unsolicited AEs).

 At Unscheduled Visits, any of the specified evaluations that are relevant to the subject may be performed at the discretion of the site PI.

**APPENDIX B: TABLE FOR GRADING THE SEVERITY OF ADVERSE EVENTS**

PARAMETER	GRADE 1 - MILD	GRADE 2 - MODERATE	GRADE 3 - SEVERE
Clinical adverse event NOT identified below	Mild symptoms causing no or minimal interference with usual social and functional activities with intervention not indicated	Moderate symptoms causing greater than minimal interference with usual social and functional activities with intervention indicated	Severe symptoms causing inability to perform usual social and functional activities with intervention or hospitalization indicated
Vital signs			
Temperature	38.0 to <38.6°C	38.6 to <39.3°C	≥39.3°C
Blood pressure	140 – 159 mmHg systolic OR 90 – 99 mmHg diastolic	160 – 179 mmHg systolic OR 100 – 109 mmHg diastolic	≥180 mmHg systolic OR ≥110 mmHg diastolic OR hospitalization indicated
Pulse	101-115 or 50-54 or 45-50 if baseline <60bpm	116-130 or 45-49 or 40-44 if baseline <60bpm	>130 or ventricular dysrhythmias or <45 or <40 if baseline <60bpm
Respiration	23-25	26-30	≥30
Local injection site			
Pain or tenderness (report only one)	Symptoms causing no or minimal interference with usual social and functional activities	Symptoms causing greater than minimal interference with usual social and functional activities	Symptoms causing inability to perform usual social and functional activities
Erythema or redness (report only one)	2.5 to <5 cm in greatest diameter AND Symptoms causing no or minimal interference with usual social and functional activities	≥5 to <10 cm in greatest diameter OR Symptoms causing greater than minimal interference with usual social and functional activities	≥10 cm in greatest diameter OR Ulceration OR Secondary infection OR Sterile abscess OR Symptoms causing inability to perform usual social and functional activities
Induration or swelling (report only one)	2.5 to <5 cm in greatest diameter AND Symptoms causing no or minimal interference with usual social and functional activities	≥5 to <10 cm in greatest diameter OR Symptoms causing greater than minimal interference with usual social and functional activities	≥10 cm in greatest diameter OR Ulceration OR Secondary infection OR Sterile abscess OR Symptoms causing inability to perform usual social and functional activities

Systemic			
Anaphylaxis **	--	--	Symptomatic bronchospasm, with or without urticaria; parenteral intervention indicated; allergy-related edema or angioedema; hypotension
**Definition: A disorder characterized by an acute inflammatory reaction resulting from the release of histamine and histamine-like substances from mast cells, causing a hypersensitivity immune response. Clinically, it presents with breathing difficulty, dizziness, hypotension, cyanosis, and loss of consciousness, and may lead to death.			
Acute allergic reaction	Localized urticaria with no intervention indicated	Localized urticaria with intervention indicated OR Mild angioedema with no intervention indicated	Generalized urticaria OR Angioedema with intervention indicated OR Symptoms of mild bronchospasm
Hypersensitivity	Transient flushing or rash	Rash; flushing; urticaria; dyspnea	Symptomatic bronchospasm with or without urticaria; parenteral medication indicated; allergy-related edema or angioedema; hypotension
Fever	38.0 to <38.6°C or 100.4 to <101.5°F	≥38.6 to <39.3°C or ≥101.5 to <102.7°F	≥39.3°C or ≥102.7°F
Chills	Symptoms causing no or minimal interference with usual social and functional activities	Symptoms causing greater than minimal interference with usual social and functional activities	Symptoms causing inability to perform usual social and functional activities
Headache	Symptoms causing no or minimal interference with usual social and functional activities	Symptoms causing greater than minimal interference with usual social and functional activities	Symptoms causing inability to perform usual social and functional activities
Myalgias (generalized)	Symptoms causing no or minimal interference with usual social and functional activities	Symptoms causing greater than minimal interference with usual social and functional activities	Symptoms causing inability to perform usual social and functional activities
Fatigue or Malaise (report only one)	Symptoms causing no or minimal interference with usual social and functional activities	Symptoms causing greater than minimal interference with usual social and functional activities	Symptoms causing inability to perform usual social and functional activities

Decreased appetite	Loss of appetite without decreased oral intake	Loss of appetite associated with decreased oral intake without significant weight loss	Loss of appetite associated with significant weight loss
Dermatological			
Skin rash	Localized rash	Diffuse rash OR Target lesions	Diffuse rash AND Vesicles or limited number of bullae or superficial ulcerations of mucous membrane limited to one site
Gastrointestinal			
Nausea	Transient (< 24 hours) or intermittent AND No or minimal interference with oral intake	Persistent nausea resulting in decreased oral intake for 24-48 hours	Persistent nausea resulting in minimal oral intake for > 48 hours OR Rehydration indicated (e.g., IV fluids)
Vomiting	Transient (< 24 hours) or intermittent AND No or minimal interference with oral intake	Frequent episodes with no or minimal dehydration	Persistent vomiting resulting in orthostatic hypotension OR Rehydration indicated (e.g., IV fluids)
Diarrhea	Transient or intermittent episodes of unformed stools OR Increase of ≤ 3 stools over baseline per 24-hour period	Persistent episodes of unformed to watery stools OR Increase of 4-6 stools over baseline per 24-hour period	Increase of ≥ 7 stools over baseline per 24-hour period OR IV fluid replacement indicated
Abdominal discomfort	Symptoms causing no or minimal interference with usual social and functional activities	Symptoms causing greater than minimal interference with usual social and functional activities	Symptoms causing inability to perform usual social and functional activities

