### **9.2 Methods and Timing for Assessing, Recording, and Analyzing Safety Parameters**

#### **9.2.1 Adverse Events**

##### **Adverse Event:**

ICH E6 GCP defines an AE as any untoward medical occurrence in a clinical research subject administered a study drug regardless of its causal relationship to the study drug. An AE can therefore be any unfavorable and unintended sign (including an abnormal laboratory finding), symptom, or disease temporally associated with the use of the study drug. The occurrence of an AE may come to the attention of study personnel during study visits and interviews of a study subject presenting for medical care or upon review by a study monitor. Since the safety profile of BPG (both 1 and 3 doses) is well established, and this study is not powered to detect new, unknown safety signals, non-serious AEs will not be reported to the DSMB.

All AEs not meeting the criteria for SAEs should be captured on the appropriate eCRF. Information to be collected includes event description, time of onset, clinician's assessment of severity, relationship to study drug (assessed only by those with the training and authority to make a diagnosis), and time of resolution/stabilization of the event. All AEs occurring while on study must be documented appropriately regardless of relationship. All AEs will be followed to adequate resolution.

Any medical condition that is present at the time that the subject is screened should be considered as a baseline finding and not reported as an AE. However, if it deteriorates at any time during the study, it should be recorded as an AE.

All AEs must be graded for severity and relationship to the study drug.

The US Food and Drug Administration (FDA) defines an AE as any untoward medical occurrence associated with the use of a drug in humans, whether or not considered drug-related.

**Severity of Event:** All AEs will be assessed by the clinician using a protocol-defined grading system (see Appendix B).

Changes in the severity of an AE should be documented to allow an assessment of its duration at each level of intensity to be performed. AEs characterized as intermittent require documentation of onset and duration of each episode.

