### 9.2.3 Serious Adverse Events

#### **Serious Adverse Event (SAE):**

An AE or suspected adverse reaction is considered "serious" if, in the view of either the investigator or sponsor, it results in any of the following outcomes:

- death,

- 
- a life-threatening AE\*,
  - inpatient hospitalization or prolongation of existing hospitalization,
  - a persistent or significant incapacity or substantial disruption of the ability to conduct normal life functions, or
  - a congenital anomaly/birth defect.
  - Important medical events that may not result in death, be life-threatening, or require hospitalizations may be considered serious when, based upon appropriate medical judgment, they may jeopardize the subject and may require medical or surgical intervention to prevent one of the outcomes listed in this definition. Examples of such medical events include allergic bronchospasm requiring intensive treatment in an emergency room or at home, blood dyscrasias or convulsions that do not result in inpatient hospitalization, or the development of drug dependency or drug abuse.

\* An AE is considered “life-threatening” if, in the view of either the investigator or sponsor, its occurrence places the subject at immediate risk of death. It does not include an AE that, had it occurred in a more severe form, might have caused death.

All SAEs will be:

- Assessed for severity and relationship to the study drug and alternate etiology (if not related to the study drug) by a licensed study physician.
- Recorded on the appropriate SAE form and eCRF.
- Followed through resolution by a licensed study physician.
- Reviewed and evaluated by the DSMB (periodic review unless related), DMID, and the IRB.

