## 9.6 Safety Oversight (ISM plus DSMB)

An ISM at each clinical research site will oversee the safety of research subjects at that site and will provide independent written evaluation of SAEs and related Grade 3 AEs to the PI, DMID Clinical Project Manager, and DMID Medical Monitor. The ISM will serve as an independent consultant for the site PI on subject-related issues. The ISM will communicate with the site PI and study PIs to resolve any issues.

Safety oversight will be conducted by a DSMB that is an independent group of experts that monitors subject safety and advises DMID. The DSMB members will be separate and independent of study personnel participating in this trial and should not have scientific, financial, or other conflict of interest related to the study. The DSMB will consist of members with appropriate expertise to contribute to the interpretation of the data from this trial.

The DSMB will review safety and enrollment data when half of the study subjects have been enrolled and observed for SAEs through the Month 1 Visit.

The DSMB will review study progress and subject clinical and safety data at the following time points:

- At least annually after the first subject is enrolled.
- Ad hoc when a halting rule is met, for immediate concerns regarding observations during the study, or as needed.
- During a final closeout meeting, held at the end of the study after the database is locked to review cumulative study data prior to finalizing the Clinical Study Report (CSR).

The DSMB will operate under the rules of a DMID-approved charter that will be written at the organizational meeting of the DSMB. As an outcome of each review/meeting, the DSMB will make a recommendation as to the advisability of proceeding with study administrations (as applicable), and to continue, modify, or terminate the study.

DMID or the DSMB chair may convene the DSMB on an ad hoc basis according to protocol criteria or if there are immediate concerns regarding observations during the study. The DMID Medical Monitor is empowered to stop enrollment and study treatment if SAEs that meet the halting criteria are reported. The DMID Medical Monitor will be responsible for reviewing SAEs in real time. The DSMB will review SAEs on a regular basis and *ad hoc* during the study.

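### Appendix B puts a respiratory rate of exactly 30 in both Grade 2 and Grade 3, the line at which a non-serious related event needs the Independent Safety Monitor's written evaluation

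*Protocol*

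**What the plan says.** Section 9.2.1 of the protocol makes Appendix B the system by which clinicians grade every adverse event.

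**Respiration row.** Grade 1 is 23-25, Grade 2 is 26-30, and Grade 3 is 30 or more.

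**Allergic rows.**
- Acute allergic reaction, Grade 2, includes "Mild angioedema with no intervention indicated". Grade 3 of that row covers angioedema that does need intervention, and also "Generalized urticaria".
- Hypersensitivity, Grade 2, reads "Rash; flushing; urticaria; dyspnea". Its Grade 3 cell ends with "allergy-related edema or angioedema; hypotension", with no condition on mildness or intervention.
- Anaphylaxis has the same angioedema entry at Grade 3, but it alone of the three carries a definition, which begins "A disorder characterized by an acute inflammatory reaction resulting from the release of histamine and histamine-like substances from mast cells".

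**What Grade 3 triggers.** Under Section 9.6 the Independent Safety Monitor at each site "will provide independent written evaluation of SAEs and related Grade 3 AEs". Section 5.3.3 lists a related Grade 3 event among the reasons for which an Arm 2 subject may be taken off further doses after discussion with the investigator. Serious events follow their own route whatever their grade. Section 9.2.3 has them "Reviewed and evaluated by the DSMB (periodic review unless related), DMID, and the IRB", and Section 9.6 sends them to the Monitor.

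**The concern.** A grading table should give each presentation one grade. At a rate of 30 this one gives two, and the two fall on either side of a line that the protocol uses. Section 9.2.1 says that non-serious events are not reported to the DSMB, so for a related non-serious event the Monitor's written evaluation is the main independent review provided, and Grade 3 decides whether it is required. Two of the ten sites could follow the table to the letter and handle the same event differently.

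The allergic rows raise a softer version of the same question. Section 2.3.1 names rash and hypersensitivity reactions as the most common adverse events caused by penicillin, and Arm 2 subjects are dosed again at Weeks 1 and 2. The grade given to a first reaction is therefore of some practical interest.

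**Working it through.** No design figure is involved, so there is nothing to reproduce. The check compares ranges and entries in Appendix B.

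**1. Respiration.** Grade 2 holds 30 − 26 + 1 = 5 whole numbers: 26, 27, 28, 29 and 30. Grade 3 holds 30, 31 and so on. Their intersection is {30}, so 1 of the 5 Grade 2 values also meets Grade 3.

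| Rate | As printed | If Grade 2 is 26-29 | If Grade 3 is above 30 |
|---|---|---|---|
| 23-25 | 1 | 1 | 1 |
| 26-29 | 2 | 2 | 2 |
| 30 | 2 and 3 | 3 | 2 |
| 31 and above | 3 | 3 | 3 |

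Either change leaves one grade per value.

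The rows around it meet without overlap at the same line: temperature (below 39.3 °C, then 39.3 °C or more), systolic pressure (up to 179, then 180), diastolic pressure (up to 109, then 110) and fast pulse (up to 130, then above 130). The overlap in Respiration is therefore a slip and not the table's convention.

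**2. Allergic rows.** The Acute allergic reaction row is consistent on its own: whether intervention is indicated separates Grade 2 from Grade 3 angioedema. The difficulty arises only when the same event is placed in the Hypersensitivity row instead, and only if the semicolons in its Grade 3 cell separate alternatives. That reading is natural, because the Grade 2 cell of the row is built the same way and would otherwise require rash, flushing, urticaria and dyspnea all at once.

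| Presentation | Acute allergic reaction | Hypersensitivity | If the higher grade prevails | If the more specific cell governs |
|---|---|---|---|---|
| Mild angioedema, no intervention | 2 | 3 | 3 | 2 |
| Generalized urticaria | 3 | 2 (urticaria, unqualified) | 3 | 3 |

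Urticaria comes out at Grade 3 under either rule. Angioedema depends on the rule chosen, and the protocol states none.

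**3. Reach.**
- Serious events go to the Monitor at any grade (9.6), so only non-serious related events are affected.
- Halting turns on a related serious event or an overall pattern of clinical events (9.5), not on Grade 3.
- Section 11.4.3 specifies summaries by severity for solicited events. Respiratory rate and angioedema are not among these (8.1, 9.2.2).
- The efficacy analyses and sample size (11.2, 11.4.4) do not use adverse event grades.

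**The case against.** The overlap at 30 is hard to dispute. The case on the other side concerns the allergic rows and the size of the effect.

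A reader might infer that Appendix B contradicts itself on angioedema just as plainly as on respiration. The documents do not support that. The two grades sit in differently named rows, and they collide only if the semicolons mean *or*, whereas the neighbouring Acute allergic reaction row prints an explicit OR where it wants alternatives. Letting the more specific cell govern would settle both urticaria and angioedema. The table already needs that rule elsewhere: in the Pulse row, 40-44 with a baseline below 60 is Grade 2 although any rate below 45 is Grade 3, which works only if the baseline-specific limit overrides the general one. This objection stands, and it makes the allergic rows a secondary point. What remains is that the protocol does not state the rule and that two of the three allergic rows have no definition.

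A reader might also infer that the overlap determines who is taken off Arm 2 treatment. It does not. Stopping is optional under Section 5.3.3, and investigator's discretion is a separate listed reason.

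The number of events is likely to be small. Known or suspected penicillin or beta-lactam allergy is excluded (5.2), and important medical events can be classed as serious on medical judgment (9.2.3). Every event is recorded with severity and relatedness in any case. All of this stands and limits the point to a minor one.

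Finally, sites may simply choose the higher grade at 30. That would be sensible, but the protocol does not tell them to.

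**Conclusion.** The respiration overlap is a definite error, confined to one value. Its consequence is that one non-serious related event may or may not require the Monitor's written evaluation, depending on which of two printed cells a site applies. The specificity rule that could settle the allergic rows does not help here, because neither cell is more specific than the other.

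The allergic-row ambiguity is real but weaker. It rests on how a site names the event, on how the semicolons are read, and on the absence of a stated precedence rule.

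The protocol gives no rate for allergic reactions or for raised respiratory rate, so the number of subjects affected cannot be calculated. That it is small is a judgment from the exclusion criteria and the route for serious events. Overall severity is minor, and no conclusion about efficacy, power or halting depends on it.

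**What to change.** - **Respiration:** change Grade 2 to 26-29, or Grade 3 to above 30. The medical monitor should confirm which is intended, since the first makes a rate of 30 Grade 3 and the second makes it Grade 2.
- **Allergic rows:** add one sentence stating either that the more specific cell governs or that the higher grade prevails. If the second, confine it to the allergic rows. Applied to the whole table, it would turn a pulse of 40-44 in a subject with a baseline below 60 into Grade 3, against the evident intent of that row. Alternatively, limit the Hypersensitivity Grade 3 entry to angioedema with intervention indicated; this settles angioedema but leaves urticaria open. Merging the rows is not needed.
- **Cost:** a one-cell correction, one added sentence and a notice to sites. Any events already graded at a rate of 30, or under the two allergic rows, should be checked again. The protocol does not show how many there are.
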